9.6 Additional Study Restrictions

The following additional restrictions will be in place for the duration of the study:

1. Subjects must abstain from alcohol during the 24 h prior to screening and the 24 h prior to admission until discharge from the study
2. Subjects must not drink liquids or eat food containing grapefruit, cranberry, caffeine or other xanthines from 24 h prior to admission until discharge from the study
3. Subjects should refrain from eating food containing poppy seeds for 48 h prior to screening and for 48 h prior to admission until discharge from the study
4. Subjects must not take part in any unaccustomed strenuous exercise from the 72 h before the screening visit and then from 72 h prior to admission until discharge from the study

The additional restrictions above are not exclusion criteria; if non-compliance occurs, a protocol deviation will be completed.

10 Study Procedures

Study procedures will be performed as detailed in the study schedule of assessments in [Appendix 2](#), and in accordance with Quotient Sciences standard operating procedures (SOPs) unless otherwise stated in this protocol.

10.1 Screening

Within the 28 days preceding first dose, all subjects will be required to undergo a screening visit. Screening procedures will be carried out in accordance with the study flow chart in [Appendix 2](#).

If the start of the study is delayed for any reason so that the interval between screening and first dose exceeds 28 days, all or part of the screening procedures may be repeated at the discretion of the investigator.

Subjects previously screened generically may participate in this study provided they meet the subject selection criteria. Procedures required by this protocol will only be done if they were not performed during generic screening. All screening data must be obtained within 28 days prior to administration of study medication, as stipulated above.

Screening safety procedures such as safety bloods, ECGs, vital signs, carbon monoxide breath tests, alcohol breath tests and urinalysis can be repeated as clinically indicated under the discretion of the investigator or sub-investigator if there is a concern regarding a subject's safety or eligibility to participate in the trial.

10.1.1 Subject Re-Screening

This study permits the re-screening of a subject who has discontinued the study as a pre-treatment failure (ie subject has not been treated); the reason for failure must be temporary and expected to resolve. If re-screened, the subject must be re-consented.

10.2 Admission and Pre-dose Procedures

The admission and pre-dose procedures are presented in [Appendix 2](#).

The identity of the subjects will be confirmed at admission and pre-dose.

In addition, the ongoing eligibility of subjects will be re-assessed at admission/pre-dose, as described in [Sections 9.2](#) and [9.3](#).

Admission safety procedures such as safety bloods, ECGs, vital signs, urinalysis and drugs of abuse tests can be repeated as clinically indicated under the discretion of investigator or sub-investigator if there is a concern regarding a subject's safety or eligibility to participate in the clinical trial.

The subjects will be admitted to the clinical unit on the evening before dosing (Day -1).

10.3 Study Day Procedures

10.3.1 Blood Volume

The total blood volume for each subject will not exceed 550 mL in a 4 week period.

The first 0.5 mL of blood withdrawn via cannula will be discarded.

10.3.2 Timing of Procedures

There are times where the protocol requires more than one procedure to be completed at the same time point. In these instances the following will apply to post-dose time points:

PK samples should take priority over other procedures scheduled at the same time point.

As guidance, the preferred order of assessments is:

ECGs should be taken prior to vital signs when both measurements are scheduled at the same time point. Other assessments, eg physical examinations, will be performed within the required time windows.

All safety assessments will be timed and performed relative to the start of dosing.

10.3.3 Discharge from the Clinical Unit

A subject will be allowed to leave the premises without additional investigator or delegate review, following completion of study-specific procedures at discharge, providing that:

- no AEs have been reported during the study visit
- the subject responds in the affirmative when asked if they are feeling well

Subjects will be dosed on the morning of Day 1 following an overnight fast and will remain resident in the clinical unit until up to 168 h after dosing (Day 8). It is planned that subjects will be released as a group when all subjects have achieved a mass balance cumulative recovery of >90% or if <1% of the dose administered has been collected in urine and faeces within 2 separate, consecutive 24 h periods. This may result in the subjects being discharged as a group prior to completion of the planned residency period. Once the discharge criteria or the planned residency period has been achieved, subjects will undergo discharge assessments and collection of all samples (blood, urine and faeces) will be stopped. If mass balance criteria have not been met by all subjects on Day 8, the residency period for the subjects not achieving the release criteria may be extended up to a maximum of 48 h post-dose (Day 10) for further collection of urine and/or faeces. If the criterion is still not met by Day 10, or if additional residency is not considered appropriate or necessary, then home collections of urine and/or faeces may be requested at the discretion of the investigator for individual subjects.

If any of these conditions are not met, then the subject will only be allowed to leave the clinical unit with the authorisation of the investigator or appropriately qualified delegate.

There will be no continued provision of the study intervention or treatment for subjects as this study involves healthy volunteers only.

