Subjects will be dosed on the morning of Day 1 following an overnight fast and will remain resident in the clinical unit until up to 168 h after dosing (up to Day 8). It is planned that subjects will be released as a group when all subjects have achieved a mass balance cumulative recovery of >90% or if <1% of the dose administered has been collected in urine and faeces within 2 separate consecutive 24 h periods. This may result in the subjects being discharged as a group prior to completion of the planned residency period. Once the discharge criteria or the planned residency period have been achieved, collection of all samples (blood, urine and faeces) will be stopped and the subjects will undergo discharge assessments. If the mass balance criteria have not been met by all subjects by Day 8, the residency period for the subjects not achieving the release criteria may be extended up to a maximum of an additional 48 h (up to Day 10) for further collection of urine and/or faeces. If the release criteria have still not been met by Day 10, or if any additional residency is not considered appropriate or necessary, then home collections of urine and/or faeces may be requested at the discretion of the investigator for individual subjects.

Number of Subjects Planned:

It is planned to enrol 6 healthy male subjects to ensure data in 4 evaluable subjects. A subject will be considered evaluable if they have provided mass balance and PK samples for up to 72 h (up to Day 4) after IMP administration, or have demonstrated >90% mass balance recovery, or have <1% of the administered dose eliminated in excreta for 2 consecutive days, whichever is sooner. No replacement subjects are to be used in this study.

Duration of Study:

Single oral dose administration on a single occasion. The estimated time from screening until the end of the study is approximately up to 6 weeks.

Main Inclusion Criteria:

Healthy males aged 30 to 65 years.
 Body mass index (BMI) 18.0 to 30.0 kg/ m².

Investigational Medicinal Product, Dose and Mode of Administration:

The following IMP will be used in this clinical study.

| Treatment | IMP Name | Dose | Route of Administration |
|-------------|-----------------------------------|--|-------------------------|
| Single dose | [¹⁴ C]-MD1003 Capsule | 100 mg (NMT 2.22 MBq; 60.0 µCi ¹⁴ C) | Oral, fasted |

¹⁴C: carbon 14, NMT: not more than

All doses will be administered orally with 240 mL water, following an overnight fast.

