8.1 Study Plan

[figure not shown]
This is a single-centre, open-label, non-randomised, single oral dose study in healthy male subjects. It is planned to enrol 6 subjects to ensure 4 evaluable subjects.

Each subject will receive a single oral administration of a capsule containing 100 mg MD1003 and NMT 2.22 MBq (approximately 60.0 µCi) [¹⁴C], in the fasted state.

The study design is presented in [Figure 1](#). Subjects will be screened to participate in the study up to 28 days before dosing. Subjects will be admitted to the clinical unit on the evening of Day -1 prior to IMP administration.

Subjects will be dosed on the morning of Day 1 following an overnight fast and will remain resident in the clinical unit until up to 168 h after dosing (up to Day 8). It is planned that subjects will be released as a group when all subjects have achieved a mass balance cumulative recovery of >90% or if <1% of the dose administered has been collected in urine and faeces within 2 separate consecutive 24 h periods. This may result in the subjects being discharged as a group prior to completion of the planned residency period. Once the discharge criteria or the planned residency period has been achieved, collection of all samples (blood, urine and faeces) will be stopped and the subjects will undergo discharge assessments. If the mass balance criteria have not been met by all subjects by Day 8, the residency period for the subjects not achieving the release criteria may be extended up to a maximum of an additional 48 h (up to Day 10) for further collection of urine and/or faeces. If the release criteria have still not been met by Day 10, or if any additional residency is not considered appropriate or necessary, then home collections of urine and/or faeces may be requested at the discretion of the investigator for individual subjects.

Figure 1 Study Sequence

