^a Subject may be discharged as a group earlier if a cumulative recovery of >90% has been achieved or if <1% of the dose administered has been collected in urine and faeces within 2 separate consecutive 24 h periods. If the criteria are not met by Day 8, this may result in the extension of the residency period for the subjects not achieving the release criteria up to a maximum of an additional 48 h (up to Day 10) for further collection of urine and/or faeces. If the criteria are still not met by Day 10, or if additional residency is not considered appropriate or necessary, then home collections of urine and/or faeces may be requested at the discretion of the investigator for individual subjects.

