8.4 Subject Replacement

No replacement subjects are to be used in this study.

A subject will be considered evaluable if they have provided mass balance and PK samples for up to 72 h (up to Day 4) after IMP administration, or have demonstrated >90% mass balance recovery, or have <1% of the administered dose eliminated in excreta for 2 consecutive days, whichever is sooner.

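### Does Section 10.3.3, by capping extended residency at 48 h after dosing, cut off late excreta collection in subjects with incomplete recovery?

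*Protocol*

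**What the plan says.** Section 10.3.3 of the Protocol sets the clock: "Subjects will be dosed on the morning of Day 1 following an overnight fast", and subjects "will remain resident in the clinical unit until up to 168 h after dosing (Day 8"). If the mass balance criteria have not been met by all subjects on Day 8, residency for those who have not met them "may be extended up to a maximum of 48 h post-dose (Day 10) for further collection of urine and/or faeces". The following sentence deals with subjects who still fail the criterion at Day 10, or for whom a longer stay is judged inappropriate or unnecessary. For them the investigator may request home collection.

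The same provision appears in four other places:

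- Synopsis, Study Design: residency "may be extended up to a maximum of an additional 48 h (up to Day 10) for further collection of urine and/or faeces".
- Section 8.1, Study Plan: "may be extended up to a maximum of an additional 48 h (up to Day 10").
- Note a to Figure 1 in Section 8.1: "up to a maximum of an additional 48 h (up to Day 10) for further collection of urine and/or faeces".
- Note a to the study flow chart (Appendix 2): the same wording as the Figure 1 note.

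Section 10.3.3 is the only one of the five that counts the 48 h from dosing. The other four count it from the end of the planned residency. All five give Day 10.

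**The concern.** The clause contradicts itself. A stay that has already lasted 168 h cannot be extended to 48 h, and 48 h after dosing does not fall on Day 10. It also disagrees with four other statements of the same rule.

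The location makes this look serious. Section 10.3.3 is the discharge section, and the limit decides how long urine and faeces can be collected in the unit from subjects whose recovery is still incomplete on Day 8. Cumulative recovery in excreta is a primary endpoint. Only 6 subjects are enrolled, 4 evaluable subjects are needed, and none will be replaced. If staff followed the hour figure, no extension could be given and the 168–216 h collection would be missed in the subjects where recovery is least complete. If they kept subjects to Day 10, they could be said to breach the hour limit, and Section 17.2 does not accept waivers.

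**Working it through.** **Inputs.** Dosing on the morning of Day 1 is 0 h (Section 10.3.3). Planned residency is 168 h, labelled Day 8 (Section 10.3.3). The disputed cap is 48 h after dosing, labelled Day 10 (Section 10.3.3). The cap elsewhere is 48 h more than the planned residency, also labelled Day 10 (Synopsis, Section 8.1, Figure 1 note, flow-chart note).

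**Formula.** Study day = 1 + hours after dosing / 24.

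**Check of the formula against the Protocol's other pairs.**

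- Section 8.4 counts a subject as evaluable who has "provided mass balance and PK samples for up to 72 h (up to Day 4) after IMP administration": 1 + 72/24 = Day 4. Reproduced.
- Planned residency: 1 + 168/24 = Day 8. Reproduced.

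**Applied to the cap.**

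| Reading | Hours after dosing | Study day | Agrees with Day 10? |
|---|---|---|---|
| Section 10.3.3, literal | 48 | 1 + 48/24 = 3 | No |
| Other four places | 168 + 48 = 216 | 1 + 216/24 = 10 | Yes |

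The literal figure falls 168 − 48 = 120 h before the earliest time at which the clause applies, and 216 − 48 = 168 h before its own day label.

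**Can the literal reading be followed?** The clause takes effect only once Day 8 has been reached with criteria unmet. By then a Day 3 limit has already passed. The next sentence of Section 10.3.3 again treats Day 10 as the end of the extension. Only the Day 10 limit can be carried out, and it agrees with the other four statements.

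**What would be lost even on the literal reading?** Where further residency is not considered appropriate or necessary, home collection may be requested from individual subjects, so excreta after Day 8 could still be obtained. The extension is itself permissive, so the wording used elsewhere guarantees no collection either.

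**Size of the 168–216 h collection.** If excretion continued at the 1% threshold, two further days would add 2 × 1% = 2 percentage points. That figure is an assumption and not a lower bound. A subject whose recovery has not passed 90% stays unreleased unless two consecutive 24 h periods are both below 1%, so one earlier day at or above 1% is enough to miss the rule. As an illustration, 1.2% on the sixth day after dosing and 0.3% on the seventh would fail it. If later output were no higher than 0.3% a day, Days 8 to 10 would add at most 2 × 0.3% = 0.6 points. The rule describes excretion before Day 8 and does not fix what follows.

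**Evaluability.** Under Section 8.4, a subject who has provided the mass balance and PK samples to 72 h is already evaluable. The count of 4 evaluable subjects does not depend on the extension.

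**The case for a change.** The best argument for acting is that Section 10.3.3 governs release from the unit and is the only place that states the cap in hours after dosing, and that figure is wrong. The corresponding 216 h is written nowhere in the Protocol. The extension may well be used, since Section 5.3.4 raises the possibility that part of a biotin dose is retained for many days. With so few subjects and no replacements, late recovery in one person matters. Correcting the line would cost next to nothing.

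Much of this is true. The wording is wrong, the four conflicting places are correctly identified, and the five statements ought to agree. The consequences do not follow from it. Section 10 directs staff to the schedule in Appendix 2 for study procedures, and the note there carries the workable wording. A stay to Day 10 complies with the day label in Section 10.3.3 itself and with the other four places. It breaches the Protocol only on a reading that nobody could carry out, so the bar on waivers does not come into play. That an edit is cheap does not make it necessary when no collection, endpoint or conclusion would differ after it.

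**Conclusion.** This is a clerical slip, most likely the loss of the word *additional* and its replacement by a reference to dosing. The hour figure in Section 10.3.3 is off by 168 h against its own Day 10 label. Every statement of the rule, including that one, sets the same Day 10 limit, and the literal reading cannot be executed. The effect on collected excreta, on cumulative recovery, on the number of evaluable subjects and on the analysis is nil.

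This rests on two assumptions: that staff resolve the sentence by its Day 10 label, which its next sentence and four other places support, and that home collection remains open as written. The wording can be reconciled with the other four places if the Protocol is reissued for another reason. It does not by itself call for a change to the plan.

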10.3.4 Medical Supervision

A physician will be responsible for the clinical aspects of the study and will be available at all times during the study. In accordance with the current Association of the British Pharmaceutical Industry guidelines [13], each subject will receive a card stating the telephone number of the investigator and the 24/7 contact details of the Quotient on-call physician.

11 Dosing of Subjects

11.1 Food and Fluid Intake

The calorie/fat content of meals is not required to be controlled during this study, with the exception of meals on Day 1. Meals on subsequent days will be provided at nominal times.

Subjects will be allowed water up to 1 h before the scheduled dosing time and will be provided with 240 mL of water at 1 h post-dose. Water will be allowed ad libitum after 1 h post-dose. Decaffeinated fluids will be allowed ad libitum from lunch time on the day of dosing.

If, for technical reasons, dosing is delayed for more than 2 h beyond the expected dosing time, subjects will receive 200 mL of Lucozade Sport at the originally scheduled dosing time, or earlier if possible.

Subjects will be provided with a light snack and then fast from all food and drink (except water) for a minimum of 8 h the day prior to dosing until approximately 4 h post-dose, at which time lunch will be provided. An evening meal will be provided at approximately 10 h post-dose and an evening snack at approximately 14 h post-dose. On subsequent days, meals will be provided at appropriate times.

If an individual subject has not experienced a bowel movement in any 36-h period post-dose, fluid intake should be increased and administration of a mild laxative (eg prune juice or a mild stool softener) should be implemented.

11.2 Administration of Test Preparations

Specific details of IMP(s) and doses to be administered are provided in [Section 5.2](#) and [Section 8.1](#), respectively. Subjects will be dosed on the morning of Day 1.

The exact time of dosing will be decided based on logistics and will be documented in the source.

Each subject will receive a single oral administration of a capsule containing 100 mg [¹⁴C]-MD1003 and NMT 2.22 MBq (60.0 µCi) on a single occasion in the fasted state.

11.3 Dosing Compliance

During all clinical phases of the study, subjects will be observed by study staff to assure compliance to all study procedures, including dose administration.

Mouth and hand checks will be conducted after dosing to ensure the capsule has been swallowed.

The date and time that each subject is dosed will be recorded in the subject's source data. Any violation of compliance will require evaluation by the investigator and sponsor to determine if the subject can continue in the study.

11.4 Prior and Concomitant Medications

No prescribed, over-the-counter medication, herbal remedies, vitamin B5 or dietary supplements containing lipoic acid will be permitted from 14 days before IMP administration until discharge from the study except 4 g per day of paracetamol and those deemed necessary by the investigator to treat AEs (see also [Section 9.3](#)). Any medications used will be recorded in the source.

Emergency equipment and drugs will be available within the clinical unit as per current standard procedures. In the unlikely event that they are required, their use will be documented.

12 Assessment of Efficacy

Not applicable for this Phase I study.

13 Assessment of Mass Balance, Pharmacokinetics, Metabolite Profiling and Identification, and Pharmacodynamics

13.1 Assessment of Mass Balance, Pharmacokinetics and Metabolite Profiling and Identification

13.1.1 Blood Sampling

Venous blood samples will be collected from the subjects by a trained member of the clinical team. Consent will be collected from the subjects for use of these samples for the purposes of the proposed study.

Plasma and whole blood samples are sent for laboratory testing in linked anonymised form (subject number only). This information is able to be linked directly to the volunteer by the Quotient research team and study monitor, however not by the laboratory staff or Sponsor.

Venous blood samples will be withdrawn via an indwelling cannula or by venepuncture according to the time schedule presented in [Appendix 2](#).

The acceptable deviations from the nominal blood sampling times are as follows:

- The pre-dose samples will be taken ≤ 1 h before dosing
- 0 to 1 h post-dose samples will be taken within ± 2 min of the nominal post-dose sampling time
- >1 to 12 h post-dose samples will be taken within ± 10 min of the nominal post-dose sampling time
- >12 h post-dose samples will be taken within ± 30 min of the nominal post-dose sampling time

Samples will be collected into appropriate tubes as specified by the bioanalytical laboratory. Details of sample tubes and processing will be contained in the Clinical Sample Processing Manual.

Samples will be shipped to Pharmaron for the analysis of total radioactivity in plasma and whole blood, and for metabolite profiling and identification in plasma. Samples will be shipped to Atlanbio for the analysis of MD1003, bisnorbiotin and biotin sulfoxide in plasma.

13.1.2 Urine Sampling

Urine samples will be collected according to the time schedule presented in [Appendix 2](#).

A single urine sample will be taken at pre-dose (the first void of the day). Where a sample is not provided, this will not be considered a deviation. All individual urine voids will be collected and shipped to the metabolism laboratory for analysis, according to Quotient Sciences SOPs, unless indicated otherwise by the sponsor.

Samples will be collected into appropriate containers as specified by the metabolism laboratory. Details of sample containers and processing will be contained in the Clinical Sample Processing Manual.

Samples will be shipped to Pharmaron for the analysis of total radioactivity and for metabolite profiling and identification.

